6.2.2 Safety Assessments

6.2.2.1 Adverse Events

Adverse Event Definition

An adverse event (AE) is any event, side effect, or other untoward medical occurrence, (including dosing errors) that may be present during treatment with a medical product or intervention and may or may not be related to that product or intervention. An AE can, therefore, be any unfavorable and unintended sign (e.g., a clinically significant abnormal laboratory finding), symptom or disease temporally associated with the use of a medicinal product or intervention, whether or not the event could be considered related to use of the product or intervention.

Clinical adverse events are illnesses, signs, or symptoms that have appeared or worsened during the study or during the follow-up period. These may include the following: 1) the exacerbation of a pre-existing illness, 2) an increase in the frequency or severity of a pre-existing event or condition, 3) any condition detected or diagnosed after study drug administration even though it may have been present prior to the start of the study or 4) continuous persistent disease or symptoms present at baseline that worsen following the start of the study. Laboratory AEs are clinically significant abnormal values obtained on laboratory tests during the acute and follow-up period.

Any medical condition or clinically significant laboratory abnormality with an onset date before the date the Informed Consent is signed is considered to be pre-existing and should be documented on the Medical History case report form (CRF.) All AEs from the time the Informed Consent is signed, whether believed to be study-related or not, must be recorded on the appropriate CRF.

It is the responsibility of the investigator to document all AEs that occur during the study. Occurrence of AEs will be assessed through observation by Investigational staff and reported on the appropriate page of the CRF.

Serious Adverse Event Definition

A Serious Adverse Event (SAE) is any untoward medical occurrence or effect that, at any dose, results in any of the following outcomes:

- Death
- Life-threatening (subject at immediate risk of death)
- Requires inpatient hospitalization or prolongation of existing hospitalization
- Results in congenital anomaly/birth defect
- Results in a persistent or significant disability or incapacity
- An important medical event that may not result in death, be life-threatening, or require

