 hospitalization may be considered a serious adverse event when, based upon
 appropriate medical judgment, it may jeopardize the subject and may require medical
 or surgical intervention to prevent one of the outcomes listed in this definition.

Documentation and Assessment of AE's and SAE's

Every adverse event, whether serious or not, must be recorded as soon as is reasonably possible in the patient's CRF. The following must be included:

- date of onset (or exacerbation in the case of worsening of an existing AE)
- frequency
- duration of effect

Additionally, the Principal Investigator (PI) must assess every adverse event in the CRF for severity and causality and must define the action taken (defined below).

Assessment of Severity (not to be confused with "seriousness")

Each AE/SAE will be assigned a category by the investigator as follows:

Mild An AE/SAE that is easily tolerated by the subject, causes minimal discomfort and does not interfere with everyday activities.

Moderate An AE/SAE that is sufficiently discomforting to interfere with normal

everyday activities; intervention may be needed.

Severe An AE/SAE that prevents normal everyday activities; treatment or other

intervention usually needed.

If there is a change in severity of an AE/SAE, it must be recorded as a separate event.

Assessment of Causality

Every effort will be made by the investigator to assess the relationship of the AE, if any, to the IMP. Causality should be assessed using the categories defined below:

Unrelated Clinical event where evidence exists that the symptom is definitely

related to etiology other than the study treatment (e.g., trauma secondary to a motor vehicle accident or a symptom suggestive of another illness which is not accepted to be a possible reaction to the

study treatment).

Unlikely Clinical event with a temporal relationship to IMP administration makes

a causal connection improbable, but that could reasonably be

explained by underlying disease or other drugs or chemicals.

Possible Clinical events with a reasonable temporal relationship to IMP

administration, but that could also be explained by concurrent disease or other drugs or chemicals that have a possible temporal relationship to the study treatment; however, a potential alternative etiology exists which may be responsible for the symptom (e.g., fever or irritability when other symptoms are present that suggest another etiology, for

example: upper respiratory infection).

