7.1.5 Safety Variables

Safety endpoints will be analyzed using the SAF.

Adverse Events

Pre-treatment adverse events and treatment adverse events will be analyzed separately. AEs will be summarized by system organ class (SOC) and preferred term (PT) according to Medical Dictionary for Regulatory Activities (MedDRA). The number of events, as well as the number and rate of affected subjects will be reported. AEs (SOC and PT) will also be summarized by seriousness, as well as by severity and relationship to study medication. No statistical testing procedures will be applied to the analysis of AEs. No statistical testing procedures will be applied to the analysis of AEs.

Incidence of Refractory Hypotension

Refractory hypotension is defined as a 20% drop in mean MAP below specific age-related criteria for more than 30 minutes. The number of subjects with any refractory hypotension from end of surgery until 48 hours will be compared between groups using Fishers' exact test. Additionally, a logistic regression analysis will be applied including factor treatment and site.

Laboratory Values (CBC with differential, serum creatinine and electrolytes & liver enzymes)

The absolute values, absolute and percentage changes from baseline will be tabulated using summary tables listing descriptive measurements for all observed time points. No statistical testing procedures will be applied to the analysis of laboratory values.

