4.5 Safety Analysis

Safety endpoints will be analyzed using the SAF.

Adverse events

Pre-treatment adverse events (PTAE) and treatment adverse events (TAE) will be analyzed separately. TAE are defined as all adverse events (AE) with time of onset or worsening on or after the time of first drug administration. If unclear due to incomplete start time / date of AE or drug administration, AEs will be assumed as TAEs.

Adverse events (AE) will be summarized by system organ class (SOC) and preferred term (PT) according to Medical Dictionary for Regulatory Activities (MedDRA) version 19.0. The number of events, as well as the number and rate of affected subjects will be reported for each treatment group. AEs will be summarized also by severity, and by relationship to study medication.

Separate analyses will be done for serious AEs and AEs leading to death.

Preferred terms of AEs with a proportion of $\geq 5\%$ in either L-citrulline or placebo group will be additionally tabulated in descending order of frequency together with the relative risk (RR), risk difference (RD), and Odds ratio (OR).

SAEs will additionally be tabulated by time of onset after time from the end of the surgery (variables "Date of surgery" and "End time" from section/CRF "Surgery"). The following timeframes will be used:

- ≤ 0 hours: Occurrence from time of first drug administration until and inclusive time of end of the surgery
- >0 to ≤ 12 hours: Occurrence after time of end of the surgery until and inclusive + 12 hours
- >12 to ≤ 24 hours: Occurrence after time of end of the surgery + 12 hours until and inclusive + 24 hours
- >24 to ≤ 36 hours: Occurrence after time of end of the surgery + 24 hours until and inclusive + 36 hours
- >36 to 48 hours: Occurrence after time of end of the surgery + 36 hours until and inclusive + 48 hours
- >48 hours: Occurrence after time of end of the surgery + 48 hours until

If unclear due to incomplete start time / date of AE or drug administration, AEs will be assigned to category >0 to ≤ 12 hours.

No statistical testing procedures will be applied to the analysis of AEs.

Incidence of refractory hypotension

Refractory hypotension is defined as dropping of mean arterial (blood) pressure below specific age-related criteria (see below) for more than 30 minutes. I.e., 2 or more successive mean arterial blood pressure (MAP) measurements within a time frame of at least 30 minutes have to be below the criteria as listed below.

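### Each severity change opens a new AE record and the SAP text gives no rule to link them, so event counts and the SAE onset table can count one episode several times

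*Protocol*

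**What the plan says.** **Recording.** Protocol 6.2.2.1, under the assessment of severity, states: "If there is a change in severity of an AE/SAE, it must be recorded as a separate event". The sentence is mandatory, covers SAEs, and does not say whether the change must be for the worse. The same section defines the scope of an AE: "Clinical adverse events are illnesses, signs, or symptoms that have appeared or worsened during the study or during the follow-up period". It requires each record to carry a "date of onset (or exacerbation in the case of worsening of an existing AE", and it starts recording at consent: "All AEs from the time the Informed Consent is signed, whether believed to be study-related or not, must be recorded on the appropriate CRF". Pre-treatment AEs are therefore in the database.

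**Reporting.** Protocol 7.1.5 says: "The number of events, as well as the number and rate of affected subjects will be reported". SAP 4.5 repeats this by arm: "The number of events, as well as the number and rate of affected subjects will be reported for each treatment group". SAP 4.5 also summarises AEs by severity and by relationship to study medication, and distributes SAEs over windows of onset relative to the end of surgery.

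**Treatment AEs (TAEs).** SAP 4.5 says: "TAE are defined as all adverse events (AE) with time of onset or worsening on or after the time of first drug administration". For unclear timing it adds: "If unclear due to incomplete start time / date of AE or drug administration, AEs will be assumed as TAEs".

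**What is absent.** SAP 4.5 has no rule that links records of one episode and no maximum-severity rule. SAP 4.8 deals with missing values, SAP 4.9 limits the blind data review to protocol deviations and analysis-set allocation, and SAP section 5 lists no change to AE handling.

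**The concern.** The recording rule makes the record the unit of data, and the analysis reports records as events. Nothing between the two turns records back into episodes. The event count then measures regradings as well as occurrences: an arm whose episodes last longer, or are regraded more often, shows more events for the same number of episodes. The severity table can list the same child for the same preferred term in more than one row. The SAE onset table, meant to show when serious events arise after surgery, can show one continuing event arising two or three times. Hypotension, the one potential AE that the protocol names for L-citrulline, is a condition whose severity can plausibly fluctuate.

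**Working it through.** The plan states no AE count, so there is no figure to reproduce. The check is a counting rule applied to the text, plus a range for the one unknown input.

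**1. Events per episode.** If an episode has k recorded severity changes, the Protocol 6.2.2.1 rule gives k + 1 records and SAP 4.5 reports k + 1 events. The number of affected children is 1. The value of k depends on how the rule is read:

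| Illustrative course (not from the documents) | Any change opens a record | Only worsening opens a record | Children affected |
|---|---|---|---|
| mild, severe, mild | 2 + 1 = 3 | 1 + 1 = 2 | 1 |
| mild, severe, moderate, mild | 3 + 1 = 4 | 1 + 1 = 2 | 1 |
| mild, moderate, severe, moderate, mild | 4 + 1 = 5 | 2 + 1 = 3 | 1 |

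The literal wording supports the second column. The third column follows if the rule is read together with the AE definition and the dating requirement, which mention only appearance and worsening. Both give more than one event per episode.

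**2. Average inflation.** Let p be the proportion of episodes that are regraded and c the number of recorded changes in each. Mean events per episode = (1 − p) × 1 + p × (1 + c) = 1 + p × c. The documents give neither p nor c, so both are assumptions:

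| p | c = 1 | c = 2 |
|---|---|---|
| 10% | 1 + 0.1 × 1 = 1.1 | 1 + 0.1 × 2 = 1.2 |
| 30% | 1 + 0.3 × 1 = 1.3 | 1 + 0.3 × 2 = 1.6 |
| 50% | 1 + 0.5 × 1 = 1.5 | 1 + 0.5 × 2 = 2.0 |

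**3. SAE onset windows.** For worsening, the dating is settled: the new record carries the date of exacerbation. Take an SAE that starts in theatre and worsens 20 hours after the end of surgery. It gives one SAE in the window up to the end of surgery and a second in the 12-to-24-hour window, although only one event began.

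**4. A pre-treatment AE that improves after dosing.** The TAE definition needs onset or worsening at or after first dose, and improvement is neither. If a record is opened for the improvement, its class depends on a date that the protocol does not prescribe:
- dated at the change: it has an onset after first dose and would be a TAE;
- original onset carried over: it stays pre-treatment;
- start incomplete and timing unclear: the SAP default makes it a TAE.

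The documents do not say which of these applies.

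**The case against.** The case for leaving the plan alone has four parts.

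- **The effect is confined to descriptive tables.** This stands. No AE is tested, and the number and percentage of affected children appear beside the event counts. The table of preferred terms reaching 5% in either arm rests on proportions of subjects. A reader might infer that hypotension results are distorted. The refractory hypotension analysis does not support that: it counts children from MAP readings and compares them by Fisher's exact test and logistic regression, so AE splitting does not reach it.
- **Only worsening should open a record.** This is a fair reading of the section as a whole, and it lowers the count. It does not remove the multiple counting, and the sentence itself says change, not worsening.
- **Nothing shows that regrading differs by arm.** This also stands. The trial is double-blind and the documents hold no data on regrading. Longer intensive care in one arm could give more chances to regrade, but that is a possibility and not a finding.
- **The rule may exist elsewhere.** The CRF and SAP Appendix A were not supplied and could contain a linking or maximum-severity rule. The point is therefore limited to the supplied text.

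A reader might also infer that any pre-treatment AE that improves after dosing is turned into a treatment AE. The documents do not support that as a result. It follows only if the new record is dated at the change, or if its start is incomplete and the timing unclear.

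**Conclusion.** The concern holds for event counts, the severity table and the SAE onset table. With the stated recording rule and no linking rule in the supplied SAP text, an episode with k recorded changes counts as k + 1 events. Over the assumed range (10% to 50% of episodes regraded, one or two changes each) this is 1.1 to 2.0 events per episode. No single value in that range should be quoted as the expected inflation, because the documents give no regrading frequency.

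Multiple records alone do not inflate the overall number or percentage of affected children, and no error rate is involved. The classification of improving pre-treatment AEs is a separate ambiguity. Where it did produce a false TAE, it would also add an affected child for that term. The point does not touch the efficacy conclusions, but it is worth correcting because the reported counts would not mean what a reader takes them to mean.

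**What to change.** Add one paragraph to SAP 4.5:

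1. For event counts, link contiguous records of the same preferred term in the same child that differ only by a severity change, and count them as one event. Keep a recurrence after resolution as a separate event.
2. Tabulate severity at the maximum per linked event, and per child and preferred term. For TAEs, use the maximum on or after first dose.
3. Class a pre-treatment event as a TAE only if its severity increases on or after first dose, and date it at that first post-dose worsening. State that a record opened for improvement keeps its original onset and is not a TAE.
4. Date all other linked events at first onset, and apply the linkage before the SAE onset table is built.

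The dating rule in item 3 is needed because the earliest SAE window begins at first drug administration. A pre-treatment SAE that worsens after dosing would fit no window if it were dated at its first onset.

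The cost is a linking step in the AE dataset and a review of record pairs, to be added to the planned blind data review. First check that the CRF and SAP Appendix A do not already contain such a rule, and that the CRF dates are enough to tell a regrade from a recurrence.

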6.2.2.2 Clinical Laboratory Variables

The laboratory analyses will be performed at the local hospital/institution laboratories. Reference ranges will be supplied by all appropriate laboratory facilities and used by the investigator to assess the laboratory data for clinical significance and pathological changes. The following laboratory tests will be performed:

Asklepion GROWTH HEALTH PINNOVATION

11 August 2017

Hematology

Hemoglobin, hematocrit, red blood cell (RBC) count, white blood cell (WBC) count (total and differential), platelet count

Serum Electrolytes, BUN, and creatinine

Serum electrolytes (Na, K, Ca, Mg and CI), BUN, and creatinine

Liver function tests

Bilirubin (total), AP, AST, ALT, and LDH

Coagulation parameter

ACT

A total amount of 16-19 mL of blood will be taken from each subject during the study for both clinical laboratory testing and citrulline plasma concentration determinations.

Urinalysis

Visual: Color, Clarity/Turbidity

Chemical: pH, Specific gravity, glucose, ketones, nitrites

Microscopic: RBCs, WBCs, epithelial cells, casts, bacteria

6.3 Appropriateness of Measurements

All efficacy and safety assessments are widely used and generally recognized as reliable, accurate and relevant to the disease condition.

7 Statistical Methods

7.1 Statistical and Analytical Plans

All aspects of statistical analyses will be detailed within a statistical analysis plan (SAP), which will be finalized prior to both data base lock and subsequent unblinding.

Continuous variables will be summarized by means, standard deviations, medians, lower and upper quartiles, minimums and maximums. Frequencies and percentages will be used to summarize categorical variables.

Analyses will be performed by visit/ time point, if not stated otherwise. Baseline will be defined

as the most recent non-missing value prior to surgery.

For time to event analyses censoring information will be used for statistical analyses. No other imputation of missing values (e.g., last observation carried forward [LOCF]) will be used, if not stated otherwise.

7.1.1 Datasets Analyzed

Safety Analysis Set (SAF)

All randomized subjects who received surgery and study medication (independent of whether it is L-citrulline or placebo) will be valid for the SAF. Within the SAF a subject will be considered for the treatment actually received and not for the treatment assigned by randomization, if different. The SAF will be used for the evaluation of the safety assessments.

Full Analysis Set (FAS)

The FAS includes all subjects who underwent surgery. Within the FAS a subject will be considered for the treatment assigned by randomization and not for the treatment actually received, if different, i.e. following the intent-to-treat (ITT) principle. The FAS will be used for the evaluation of the efficacy assessments. The FAS serves as the primary efficacy analysis set.

Modified Full Analysis Set (mFAS)

The mFAS includes all subjects who underwent surgery and received study medication (independent of whether it is L-citrulline or placebo). Within the mFAS, a subject will be considered for the treatment assigned by randomization and not for the treatment actually received, if different, i.e. following the ITT principle. The mFAS will be used for the evaluation of the efficacy assessments. The mFAS serves as a sensitivity population for the efficacy analyses.

Per-protocol Analysis Set (PP)

The PP includes all subjects included in the SAF who had no significant protocol deviations and completed through Day 28 or until discharge from the hospital (end of study follow-up). For the PP, all subjects will be assigned to the treatment actually received. The PP will only be analyzed for main efficacy outcome measures.

L-citrulline Plasma Levels

L-citrulline blood levels will be obtained on each patient at set times, and plotted and examined to confirm that they are \geq the threshold level of 100 μ mol/L.

Blind data review meeting (BDRM)

Subjects will be assigned to the SAF, FAS, mFAS, and PP during a blind data review meeting (BDRM). Further details on the analysis sets, criteria for the PP, and the DRM will be specified within the SAP.

7.1.2 Handling of Missing Data

For laboratory data, concentrations below the limit of quantification will be set to zero.

Missing safety data or safety assessments and missing plasma levels will not be estimated nor imputed. All safety summaries and analyses will be based on observed data.

Censoring procedures will be applied for all time variables as described within the sections below. Further specifications on handling of missing data are added below, as applicable.

7.1.3 Demographic and Other Baseline Characteristics

Baseline data, including demographic data will be analyzed descriptively. Patient disposition, including discontinuation and reasons for discontinuation, and subjects' exposure will be tabulated in detail. Concomitant medication will be coded according to World Health Organization (WHO) drug dictionary and tabulated accordingly.

7.1.4 Efficacy Variables

Analysis of Primary Efficacy Endpoint

The primary efficacy endpoint is a composite variable consisting of the longer of either (1) length of time on mechanical ventilation or (2) length of time of inotrope use.

The definition of mechanical ventilation includes invasive mechanical ventilation or non-invasive mechanical ventilation including BPAP or CPAP. Length of time on mechanical ventilation will be measured until the subject is discharged from the hospital or at Day 28. The length will be derived as the time in hours from separation from CPB until discontinuation of all mechanical ventilation including non-invasive support. If invasive or non-invasive mechanical ventilation is stopped but has to be restarted, time will continue to accrue. If a subject did not receive any mechanical ventilation the length is set to 0. For subjects who died before discharge from the hospital or before Day 28, respectively, the observed length of time on mechanical ventilation will be used. As sensitivity analyses subjects who died will (1) be excluded from analysis and (2) be assigned a length of time on mechanical ventilation of 28 days.

Asklepion GROWTH HEALTH PINNOVATION

11 August 2017

The definition of inotrope use includes medications which are considered within the derivation of the total inotrope score (dopamine, dobutamine, milrinone, epinephrine, phenylephrine, norepinephrine). Length of inotrope use will be measured until the subject is discharged from the hospital or until Day 28, whichever occurs first. The length will be derived as the time of first use until last use (in hours). Any duration of re-use will continue to accrue. If a subject did not use any inotropes the length is set to 0. For subjects who died before discharge from the hospital or before Day 28, respectively, the observed length on inotropes will be used. As sensitivity analyses subjects who died will (1) be excluded from analysis and (2) be assigned a length of time on inotropes of 28 days.

Hypothesis to be tested:

H0: Composite endpoint within the L-citrulline group is equal to that of the placebo group

H1: Composite endpoint within the L-citrulline group is unequal to that of the placebo group

H0 will be tested using a Wilcoxon-rank-sum test.

The level of significance is 1% (two-sided).

The FAS will be the primary analysis set for the analysis on the composite endpoint. Analyses using the mFAS and the PP serve as sensitivity analyses.

Two-sided 95% confidence intervals using Hodges-Lehman method will be additionally calculated. Survival analyses using Kaplan-Meyer estimates and plots, log-rank test and Coxregression modeling will serve as sensitivity analyses.

For survival analyses, different sets of analyses will be done:

- (1) The composite variable for subjects without any mechanical ventilation and without any use of inotropes is set to 0, observations will not be censored
- (2) The composite variable for subjects without any mechanical ventilation and without any use of inotropes is set to 0, observations will be censored
- (3) Subjects without any mechanical ventilation and without any use of inotropes will be deleted from analysis

Subjects who receive mechanical ventilation or are still using inotropes on the last day of observation (which can be Day 28, day of early discontinuation, or day of death) will be censored for survival analyses.

Analysis of Secondary Efficacy Endpoints

No formal statistical hypotheses are specified for the secondary endpoint variables. Nonetheless statistical testing methods will be applied to compare treatment groups. A significance level of 5% (two-sided) will be used for such analyses. Secondary efficacy endpoints will be analyzed using the FAS, mFAS and the PP.

Length of Time on Mechanical Ventilation

The same definitions and analyses as described for the primary endpoint will be applied.

Length of Time on Positive Pressure Ventilation

The same definitions and analyses as described for the primary endpoint will be applied.

Length of Time of Inotrope Use

The same definitions and analyses as described for the primary endpoint will be applied.

Inotrope Score

The total inotrope score at each hour post-operatively from the time of separation from bypass, until the completion of study drug will be calculated as:

Total Inotrope Score = Dopamine + Dobutamine + 10*Milrinone + 100*Epinephrine + 100*Phenylephrine + 100*Norepinephrine.

The total inotrope score will be summarized at each post-operative hour and analyzed using a Wilcoxon-Rank sum test and an analysis of variance (ANOVA) with a fixed effect for treatment group. Also, a repeated measures analysis of variance will be used to compare total inotrope score between placebo and L-citrulline over time.

Additionally, the total inotrope score over time until Day 28 or hospital discharge will be derived and analyzed using a Wilcoxon-Rank sum test and an ANOVA with a fixed effect for treatment group.

The total inotrope score will be imputed to zero after the bypass pump has been removed. It will also be imputed as zero for patients not using inotropes at all. For any missing scores between two non-missing scores they will be imputed using the most recent non-missing score (the last observation carried forward principle).

Hemodynamic Improvement

Hemodynamic evaluations include heart rate, systemic arterial blood pressure, oxygen

saturation, and central venous pressure. The absolute changes from baseline at hours 1, 2, 4, 12, 24, and 48 will be compared between groups using an ANOVA with a fixed effect for treatment group and baseline level.

An ANOVA adding site and site-by-treatment group interaction will be conducted as a sensitivity analysis. If the p-value for the site-by-treatment group interaction is lower than 0.1 the analysis will also be provided by site. Summary tables describing descriptive measurements will be generated for absolute values and absolute change from baseline values for all observed time points.

Length of time on intubation

The length will be derived as the time in hours from separation from CPB until discontinuation of intubation. Any duration of re-use of intubation will continue to accrue. If a subject did not use any intubation the length is set to 0. As a sensitivity analysis, subjects with no use of intubations will be excluded. For subjects who died before discharge from the hospital or before Day 28, respectively, the observed length of time on intubation will be used. As sensitivity analyses subjects who died will (1) be excluded from analysis and (2) be assigned a length of time on intubation of 28 days.

For the length of time on intubation the same analyses as described for the primary endpoint will be applied.

Length of PICU stay

The length of PICU stay will be calculated as the total number of days postoperative until discharge from PICU. For subjects who died before discharge from PICU or before Day 28, respectively, the observed length of PICU stay will be used. As sensitivity analyses subjects who died will (1) be excluded from analysis and (2) be assigned a length of PICU stay of 28 days.

For the length of PICU stay the same analyses as described for the primary endpoint will be applied.

Length of Time on Vasodilators

Length of time on vasodilators will be measured from first use following separation from bypass, until the subject is discharged from the hospital or at Day 28. The length will be derived as the time in hours from separation from CPB until discontinuation of all vasodilators. Any duration of re-use of vasodilators will continue to accrue. If a subject did not use any vasodilators the length is set to 0. As a sensitivity analysis, subjects with no use of vasodilators

Asklepion GROWTH HEALTH INNOVATION

11 August 2017

will be excluded. For subjects who died before discharge from the hospital or before Day 28, respectively, the observed length of time on vasodilators will be used. As sensitivity analyses subjects who died will (1) be excluded from analysis and (2) be assigned a length of time on vasodilators of 28 days.

For the length of time on vasodilators the same analyses as described for the primary endpoint will be applied.

Length of Hospitalization

The length of hospitalization will be calculated as the total number of days postoperative until discharge from the hospital. For subjects who died before discharge from the hospital or before Day 28, respectively, the observed length of hospitalization will be used. As sensitivity analyses subjects who died will (1) be excluded from analysis and (2) be assigned a length of hospitalization of 28 days.

For the length of hospitalization, the same analyses as described for the primary endpoint will be applied.

Thoracotomy Output - Duration and Volume of Chest Tube Drainage:

The total postoperative duration (in hours) that the chest tube is used will be calculated as the time from the end of the surgery to the time the chest tube is removed. If an additional chest tube is required or reinserted (until discharge from the hospital or at Day 28) the duration that the additional chest tube was used (from time of insertion to time of removal) will be added to the time the original chest tube was used for the total postoperative duration. If a subject did not use any chest tube the duration is set to 0. As a sensitivity analysis, subjects with no use of chest tube will be excluded. For subjects who died before discharge from the hospital or before Day 28, respectively, the observed duration of chest tube drainage will be used.

For the total postoperative duration, the same analyses as described for the primary endpoint will be applied. Again, as sensitivity analyses subjects who died will (1) be excluded from analysis and (2) be assigned a length of time of chest tube placement of 28 days.

The total amount of chest tube drainage (mL), added up during each duration of chest tube as described above, will be summarized using descriptive measures and compared between groups using an ANOVA with a fixed effect for treatment group.

L-citrulline Plasma Levels

Summary statistics using descriptive measures will be tabulated for plasma L-citrulline levels.

